#### **Clinical Test at Screening**

- TB Status: Tuberculin PPD skin test result, QuantiFERON-TB Gold test result, Latent TB (Yes/No)
- Hepatitis B Virus (HBV)/Hepatitis C Virus (HCV)
- Chest x-ray
  - Normal, Abnormal
  - Calcified granulomas (Absent, Present)
  - Pleural scarring (Absent, Present)
  - Pleural thickening (Absent, Present)
  - Indicative of previous TB infection (Yes, No)

[figure not shown]
## 7.2 Medical History and Prior and Concomitant Medications

Medical history data will be coded using the Medical Dictionary for Regulatory Activities (MedDRA). The actual version of the MedDRA coding dictionary will be noted in the statistical tables and clinical study report. The number and percentage of subjects in each medical history category (by MedDRA system organ class (SOC) and preferred term) will be summarized overall and by treatment group for the safety 1 Populations. The SOC will be presented in alphabetical order, and the preferred terms will be presented in alphabetical order within each SOC. Subjects reporting more than one condition/diagnosis will be counted only once in each row (SOC or preferred term).

A prior medication is defined as any medication taken prior to the date of the first dose of study drug. Prior medications will be summarized in the ITT 1 Populations.

Concomitant medications will be summarized by periods in each Safety 1 and Safety 2 Populations.

 A concomitant medication in DB Period is defined as any medication that started prior to the date of the first dose of study drug in DB Period and continued to be taken after the first dose of study drug in DB Period; or any

medications taken after the first dose of study drug and within 1 day of the last dose of study drug in DB Period.

• A concomitant medication in SB Period is defined as any medication that started prior to the date of the first dose of study drug in SB Period and continued to be taken after the first dose of study drug in SB Period or any medications, other than study drug, taken after the first dose of study drug and within 1 day of the last dose of study drug in SB Period.

The number and percentage of subjects taking medications will be summarized by generic drug name based on the World Health Organization (WHO) Drug Dictionary for both prior and concomitant medications.

#### 7.3 Protocol Deviations

Protocol deviations include eligibility criteria violations, receipt of wrong treatment or incorrect dose of study treatment, development of withdrawal criteria without being withdrawn, and use of prohibited concomitant medications. A listing of subjects with protocol deviations will be provided.

For each of the following protocol deviation categories and across all categories, the number and percentage of randomized subjects with at least one protocol deviation will be summarized overall and by the treatment groups in the ITT 1 Population:

- Subject entered into the studies or cohorts even though did not satisfy entry criteria;
- Subject developed withdrawal criteria during the study but was not withdrawn;
- Subject received wrong treatment or incorrect dose of study treatment;
- Subject took prohibited concomitant medication.

# 8.0 Handling of Potential Intercurrent Events for the Primary and Secondary Endpoints

For all the endpoints, no intercurrent event will be considered in the primary approach (treatment strategy policy), i.e., all observed data will be included in the analyses.

# 9.0 Efficacy Analyses

#### 9.1 General Considerations

[figure not shown]
The efficacy analysis will be conducted in the ITT 1 and ITT 2 Populations in DB Period and SB Period descriptively and no statistical testing will be performed in this study.

Categorical endpoints will be summarized by counts and percentages, as well as 95% confidence interval (CI) of the percentage. Continuous variables will be analyzed by the number of observations, mean, standard deviation, median, minimum, maximum, as well as 95% confidence intervals (CIs) of the mean values. The primary missing data handling approach for efficacy summary is As Observed (AO).

Table 2. Analysis Models and Imputation Methods

Period	Type of Variables	Imputation Method	Intercurrent Events Handling	Analysis Model
DB	Categorical	AO (primary)	strategy is used in this study, i.e., the occurrence of the intercurrent events (e.g., treatment discontinuation, rescue etc.) are considered irrelevant in defining the treatment effect of interest.  Under this strategy, all values for the variables of interest are used regardless of the intercurrent events.  ANCOVA includit treatment groups, stratification facto treatment groups, stratification facto AD categories [3;	Descriptive summary
	Continuous	AO (primary)		ANCOVA including DB treatment groups, baseline, stratification factors (vIGA-AD categories [3; 4] and prior use of dupilumab [yes; no]) in the model.
SB	Categorical	AO (primary)		Descriptive summary
	Continuous	AO (primary)		ANCOVA including SB treatment groups, baseline, stratification factors (vIGA-AD categories [3; 4] and prior use of dupilumab [yes; no]) in the model.

Note: Sensitivity analysis for the primary endpoint will use multiple imputation to handle missing data.

# 9.2 Handling of Missing Data

All efficacy endpoints will be analyzed using AO approach:

• The **AO analysis** will not impute values for missing evaluations, and thus a subject who does not have an evaluation at a scheduled visit will not be included in the AO analysis for that visit.

Another missing data handling method performed as a sensitivity analysis for the primary endpoint only is Multiple Imputation (MI) approach, which defined as below:

• MI approach: Markov Chain Monte Carlo (MCMC) will be first applied to augment data into monotonic missing pattern and PROC MI will be used to generate 30 datasets using the regression method. The imputation is done in two steps for the primary endpoint.

Step 1: Missing EASI scores will be imputed. The variables to be included in the imputation model are treatment groups, actual stratification factors (vIGA-AD categories (3; 4) and prior use of dupilumab (yes; no)), baseline, and measurements at each visit. The random seed for MCMC and the random seed for PROC MI are set as 1005 and 9015. The imputed post-baseline measurements will be rounded to the same precision as the observed data before the determination of responder status.

Step 2: After obtaining the EASI 90 at Week 24 based on MI imputed values, subjects will be characterized as responders or non-responders based on MI imputed datasets. The primary endpoint will be analyzed using each of the 30 datasets. SAS PROC MIANALYZE will be used to generate the final inferences of the EASI 90 percentages, the standard errors as well as 95% CIs.

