3 OBJECTIVES AND ENDPOINTS

3.1 Objectives, Hypotheses, and Estimands

Primary Objective

The primary study objectives are:

- Sub-Study 1 (SS1): The primary study objective for SS1 is to evaluate the efficacy and safety of dose escalation to upadacitinib 30 mg QD in subjects who do not achieve EASI 90 on upadacitinib 15 mg QD after 12 weeks.
- Sub-Study 2 (SS2): The primary study objective for SS2 is to evaluate the efficacy and safety of
 dose reduction to upadacitinib 15 mg QD in subjects who achieve EASI 90 on upadacitinib 30 mg
 QD after 12 weeks.

No hypothesis testing will be performed in this study.

The estimand corresponding to the primary endpoint is defined as:

 The proportion of subjects who achieve EASI 90 at Week 24, regardless of treatment discontinuation, with upadacitinib treatments (upadacitinib 15 mg or 30 mg QD) in adult subjects with moderate to severe AD.

Additional Objective

• To generate evidence on patient impact (patient reported outcomes [PROs]) with upadacitinib treatment based on a clinical response target (EASI 90) (Treat-to-Target).

This study will generate descriptive data that will provide information regarding:

- Efficacy and safety of dose escalation to upadacitinib 30 mg QD in subjects that did not achieve EASI 90 on upadacitinib 15 mg QD after 12 weeks.
- Efficacy and safety of dose reduction to upadacitinib 15 mg QD in subjects that achieve EASI 90 on upadacitinib 30 mg QD after 12 weeks.
- The effect of a treat-to-target approach based on EASI 90 response for subjects' reported itch, sleep, emotional health, and quality of life [QoL].

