5.6 Follow-Up After Subject Discontinuation of Study Drug or From Study

Discontinuation of Study Drug

Following discontinuation of study drug, the subject should be treated in accordance with the investigator's best clinical judgment based on the available approved treatment options within their country or region.

Subjects who prematurely discontinue study drug treatment will be discontinued from study participation entirely.

If a subject prematurely discontinues study drug, the procedures outlined for the Premature Discontinuation visit (PD Visit) should be completed as soon as possible, preferably within 2 weeks, and preferably prior to initiation of another therapy. In addition, a 30-Day Follow-up Visit after the last dose of study drug is required to ensure all treatment-emergent AEs/SAEs have been resolved. For subjects who prematurely discontinued study participation, this visit may be a telephone call if a site visit is not possible. A follow-up phone call following the last dose of upadacitinib during the study will not occur for subjects who begin commercially available upadacitinib.

Premature Discontinuation of Study (Withdrawal of Informed Consent)

If a subject prematurely discontinues study participation (withdrawal of informed consent) the procedures outlined for the Premature Discontinuation visit (PD visit) should be completed as soon as possible, preferably within 2 weeks and preferably prior to initiation of another therapy. In addition, if the subject is willing, a 30-day follow-up phone call after the last dose of study drug may be completed to ensure all treatment-emergent AEs/SAEs have been resolved. The follow-up phone call following the last dose of upadacitinib during the study will not occur for subjects who begin commercially available upadacitinib.

For subjects to be considered lost to follow-up, reasonable attempts must be made to obtain information on the subject's final status. At a minimum, 2 telephone calls must be made and 1 certified letter must be sent and documented in the subject's source documentation.

If a subject withdraws from study follow up or withdraws permission for the collection of their personal data, the study staff may still use available public records to obtain information about survival status only, as appropriate per local regulations.

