# 2.0 Study Objectives and Design

# 2.1 Study Objectives, Hypotheses and Estimands

The primary study objectives are:

- 1. Sub-Study 1 (SS1): The primary study objective for SS1 is to evaluate the efficacy and safety of dose escalation to upadacitinib 30 mg QD in subjects who do not achieve Eczema Area and Severity Index (EASI) 90 on upadacitinib 15 mg QD after 12 weeks.
- 2. Sub-Study 2 (SS2): The primary study objective for SS2 is to evaluate the efficacy and safety of dose reduction to upadacitinib 15 mg QD in subjects who achieve EASI 90 on upadacitinib 30 mg QD after 12 weeks.

The additional objective is to generate evidence on patient impact (patient reported outcomes [PROs]) with upadacitinib treatment based on a clinical response target (EASI 90) (Treat-to-Target).

No hypothesis testing will be performed in this study.

The estimand corresponding to the primary endpoint is defined as:

• The proportion of subjects who achieve EASI 90 at Week 24, regardless of treatment discontinuation, with upadacitinib treatments (upadacitinib 15 mg or 30 mg QD) in adult subjects with moderate to severe AD.

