# 9.3.2 Main Analysis of Primary Efficacy Endpoint

Frequencies and percentages will be provided along with 95% CIs. The AO approach will be used as the primary approach for handling the missing data. The attributes of the estimand corresponding to the primary efficacy objective are summarized in Table 3.

Table 3. Summary of the Estimand Attributes Corresponding to the Primary Efficacy Objective

		A	ttributes of th	e Estimand	
Estimand Label	Treatment	Endpoint	Population	Handling of Intercurrent Events	Statistical Summary
EASI 90 at Week 24	Upadacitinib 15 mg or 30 mg	Achievement of EASI 90 at Week 24	Subjects with moderate to severe atopic dermatitis	The treatment policy strategy is used in this study. All the values for the variable of interest will be used regardless of Intercurrent Events.	Counts and percentages will be provided along with 95% CIs.

Analysis of the primary endpoint will be conducted on the ITT 2 SS1 and ITT 2 SS2 Populations.

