# 9.3.3 Sensitivity and Supplementary Analyses of the Primary Efficacy Endpoint

[figure not shown]
The primary endpoint will be summarized using the Multiple Imputation (MI) to handle missing data.

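### The primary As Observed analysis estimates EASI 90 among single-blind entrants assessed at Week 24, which may differ in either direction from the treatment-policy estimand the plan states

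*SAP*

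**What the plan says.** Both documents define the primary estimand in the same way. SAP 2.1 has "The proportion of subjects who achieve EASI 90 at Week 24, regardless of treatment discontinuation", and Protocol 3.1 matches it. SAP 8.0 sets the strategy: "no intercurrent event will be considered in the primary approach (treatment strategy policy), i.e., all observed data will be included in the analyses". SAP Table 2 names treatment discontinuation and rescue among the events to be ignored. SAP Table 3, in 9.3.2, repeats treatment policy for the primary endpoint: "All the values for the variable of interest will be used regardless of Intercurrent Events".

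Follow-up works differently. Protocol 5.6 states: "Subjects who prematurely discontinue study drug treatment will be discontinued from study participation entirely". Under Protocol 5.4, a subject who needs systemic rescue or phototherapy stops study drug and leaves the study. A subject on topical rescue may stay on study drug.

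The main analysis is AO, in ITT_2_SS1 and ITT_2_SS2 (SAP 9.3.2). SAP 9.2 defines AO: "a subject who does not have an evaluation at a scheduled visit will not be included in the AO analysis for that visit". SAP 9.3.3 adds one sensitivity analysis: "The primary endpoint will be summarized using the Multiple Imputation (MI) to handle missing data". The imputation variables listed in SAP 9.2 are treatment group, the stratification factors, baseline and the EASI at each visit.

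**The concern.** A treatment-policy proportion needs the Week 24 outcome of people who stopped treatment. The protocol's follow-up rule means that outcome is normally not collected, and AO takes those people out of the denominator. Using all observed data does not close the gap, because the data in question are not observed. AO therefore estimates a different quantity: the EASI 90 rate among single-blind entrants who were assessed at Week 24.

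The study tests no hypothesis, so its main results are the percentages and CIs for dose escalation (SC1) and dose reduction (SC4). If these are reported under the present estimand label, they can be taken as applying to everyone who entered the cohort. The AO interval carries sampling error only and has no allowance for unassessed entrants. MI addresses them, but under a single assumption that the plan never varies.

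**Working it through.** **Inputs.**
- 454 subjects randomized 1:1, so 227 per sub-study (SAP 2.3 and 2.4).
- 54% Week 12 non-responders in SS1, which form SC1, and 65% responders in SS2, which form SC4 (SAP 2.4). The complements, 46% and 35%, form SC2 and SC3.
- Dropout of at most 8% per 12 weeks (SAP 2.4).
- Assumption: the missing share *m* of single-blind entrants is 8%. This is a planning ceiling for dropout, not a stated rate of missing Week 24 EASI.
- Assumption: AO rates *p* of 30, 50 and 70%, because the documents give no expected Week 24 rate.

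**1. The plan's own figure.** A half-width of 10 points at *p* = 0.5 needs 1.96² × 0.25 / 0.10² = 96.04 subjects, which matches the stated 96. Expected numbers assessed are 227 × 0.54 × 0.92² = 103.8 in SC1 and 227 × 0.65 × 0.92² = 124.9 in SC4, with half-widths of 9.6 and 8.8 points at 50%. The precision target for assessed subjects is met. The calculation itself removes dropouts from the Week 24 count, which fits their having no Week 24 value.

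**2. Numbers omitted at *m* = 8%.** Entered = 227 × 0.92 × share; assessed = entered × 0.92.

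| Cohort | Entered | Assessed | Missing |
|---|---|---|---|
| SC1 | 112.8 | 103.8 | 9.0 |
| SC2 | 96.1 | 88.4 | 7.7 |
| SC3 | 73.1 | 67.2 | 5.8 |
| SC4 | 135.7 | 124.9 | 10.9 |

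**3. Gap between AO and the all-entered rate.** Let *r* be the Week 24 response rate of those missing. The all-entered rate is (1 − *m*)*p* + *mr*, so AO minus all-entered is *m*(*p* − *r*).

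| Leavers' rate | *p* = 30% | *p* = 50% | *p* = 70% |
|---|---|---|---|
| *r* = *p* | 0 | 0 | 0 |
| *r* 20 points below *p* | +1.6 | +1.6 | +1.6 |
| *r* 20 points above *p* | −1.6 | −1.6 | −1.6 |
| none respond | +2.4 | +4.0 | +5.6 |
| all respond | −5.6 | −4.0 | −2.4 |

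At *m* = 4% each figure halves.

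**4. Against the AO interval.** The half-width is 1.96 × √(*p*(1 − *p*)/*n*). At 30/50/70% this is 8.8/9.6/8.8 points for *n* = 104 and 8.0/8.8/8.0 for *n* = 125. Every gap in step 3 is smaller than the half-width.

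Coverage of the all-entered rate by the AO interval is Φ(1.96 − *b*/SE) − Φ(−1.96 − *b*/SE), where *b* is the gap. With *n* = 104 and a 20-point difference it is about 93.5 to 93.8%. At the none-respond extreme it is 91.7/87.1/76.2% at *p* = 30/50/70%, and at the all-respond extreme the order reverses.

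**5. Illustration at an AO rate near 50%.**
- SC1: AO 52/104 = 50.0% (40.4 to 59.6). None respond: 52/113 = 46.0%. All respond: 61/113 = 54.0%.
- SC4: AO 62/125 = 49.6%. None respond: 62/136 = 45.6%. All respond: 73/136 = 53.7%.

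**The case against.** The strongest reply is that the plan hides nothing and already handles most of this.

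- *AO is disclosed.* SAP 9.2 says plainly who is excluded. SAP 5.0 reports how many enter each single-blind cohort, and the primary table's counts and percentages imply the AO denominator. A reader can therefore already work out how many are missing and compute crude bounds. This stands, so the extra table is mainly a matter of showing the result in the report. It does not correct the estimand label.
- *MI is planned.* It keeps every entrant, uses each subject's own earlier EASI, and carries between-imputation variance into its CI. A discontinuation effect could hardly be estimated anyway, because follow-up ends with treatment. This stands too. What remains is that the assumption about leavers cannot be checked from the data and no planned analysis varies it.
- *The extremes are unlikely.* All leavers responding is especially strained in SC1, whose members all missed EASI 90 at Week 12. This is fair: the extremes are bounds, not expectations.
- *Some leavers may have a usable value.* EASI is scheduled at the premature discontinuation visit, and one done near Day 169 might count as Week 24. Conversely, a subject can miss Week 24 without dropping out. Hence the word normally, and hence 8% is only an assumption. The SAP gives no rule for such values, but that is missing detail and does not carry this point.

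Two stronger readings are tempting. A reader might infer that AO overstates response, on the view that treatment failure drives exit. The documents do not establish this: Protocol 5.6 foresees leavers moving to other approved options and Protocol 6.1 foresees commercial upadacitinib, so their Week 24 response could be lower or higher. A reader might also join the outer limits of the two extreme SC1 intervals at 50% (46.0 − 9.2 = 36.8 and 54.0 + 9.2 = 63.2, or ±13.2) and conclude that the 10-point target fails. That span is not a confidence interval, and the target concerns assessed subjects, for whom it is met.

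**Conclusion.** The concern holds as a mismatch between estimand and primary analysis, and it should be fixed. AO estimates the EASI 90 rate among single-blind entrants assessed at Week 24 and does not by itself estimate the stated treatment-policy proportion. An error is possible, not established, and its direction is unknown.

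At 8% missing and assumed AO rates of 30 to 70%, the gap cannot exceed 5.6 points either way, and a 20-point difference in response moves the rate by only 1.6 points. With no hypothesis test, the consequence is for how the percentages and intervals are interpreted; no error rate is affected. The all-entered rate used here is also conditional: at the 8% ceiling about 18 of the 227 in each sub-study (227 × 0.08) would leave before the single-blind period and are outside ITT_2.

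**What to change.** 1. In SAP 9.3.2 and Table 3, state that AO estimates the EASI 90 rate among single-blind entrants with a Week 24 evaluation and does not by itself estimate the treatment-policy estimand. Make SAP 2.1, 8.0 and Table 2 consistent with this and record the change in SAP 14.1. Align Protocol 3.1 and 7.3 at the next amendment.
2. In SAP 9.3.3, add for each single-blind cohort the percentage and 95% CI with all ITT_2 subjects as denominator, counting first none and then all of those missing Week 24 EASI as responders. Show these beside AO and MI, with the number missing. Intermediate steps are optional, since the percentage is linear in the assumed number of responders. Label the none-respond end as a supplementary composite (non-responder) analysis. State that ITT_2 is itself conditional on entering the single-blind period.

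The cost is SAP wording and one small table. No new data are needed, and Protocol 7.4 leaves the details of sensitivity analyses to the SAP. The protocol wording can wait because any amendment needs IEC/IRB approval (Protocol 8.1). The downside is that the primary percentage will appear beside a range a few points wide.

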# 9.3 Primary Efficacy Endpoint(s) and Analyses

#### 9.3.1 Primary Efficacy Endpoint

The Primary endpoint is the achievement of EASI 90 at Week 24.

# 9.3.2 Main Analysis of Primary Efficacy Endpoint

Frequencies and percentages will be provided along with 95% CIs. The AO approach will be used as the primary approach for handling the missing data. The attributes of the estimand corresponding to the primary efficacy objective are summarized in Table 3.

Table 3. Summary of the Estimand Attributes Corresponding to the Primary Efficacy Objective

		A	ttributes of th	e Estimand	
Estimand Label	Treatment	Endpoint	Population	Handling of Intercurrent Events	Statistical Summary
EASI 90 at Week 24	Upadacitinib 15 mg or 30 mg	Achievement of EASI 90 at Week 24	Subjects with moderate to severe atopic dermatitis	The treatment policy strategy is used in this study. All the values for the variable of interest will be used regardless of Intercurrent Events.	Counts and percentages will be provided along with 95% CIs.

Analysis of the primary endpoint will be conducted on the ITT 2 SS1 and ITT 2 SS2 Populations.

# 9.3.3 Sensitivity and Supplementary Analyses of the Primary Efficacy Endpoint

[figure not shown]
The primary endpoint will be summarized using the Multiple Imputation (MI) to handle missing data.

# 9.4 Secondary Efficacy Endpoints and Analyses

## 9.4.1 Secondary Efficacy Endpoints

The secondary endpoints are:

- Achievement of EASI 75/100 at Week 24.
- Achievement of EASI 75/90/100 at Week 12.
- Achievement of EASI 90 and a Worst Pruritus NRS of 0 or 1 for subjects with Worst Pruritus NRS > 1 at Baseline at Week 12 and Week 24.

- Achievement of vIGA-AD of 0 or 1 at Week 12.
- Achievement of vIGA-AD of 0 or 1 at Week 24.
- Achievement of an improvement (reduction) in Worst Pruritus NRS  $\geq$  4 for subjects with Worst Pruritus NRS  $\geq$  4 at Baseline at Week 12.
- Achievement of an improvement (reduction) in Worst Pruritus NRS  $\geq$  4 for subjects with Worst Pruritus NRS  $\geq$  4 at Baseline at Week 24.
- Achievement of Worst Pruritus NRS of 0 or 1 for subjects with Worst Pruritus NRS > 1 at Baseline at Week 12.
- Achievement of Worst Pruritus NRS of 0 or 1 for subjects with Worst Pruritus NRS > 1 at Baseline at Week 24.
- Achievement of an improvement (reduction) from Baseline in DLQI ≥ 4 for subjects with DLQI ≥ 4 at Baseline at Week 12.
- Achievement of an improvement (reduction) from Baseline in DLQI ≥ 4 for subjects with DLQI ≥ 4 at Baseline at Week 24.
- Achievement of DLQI 0/1 for subjects with DLQI > 1 at Baseline at Week 12.
- Achievement of DLQI 0/1 for subjects with DLQI > 1 at Baseline at Week 24.

